4.5. Sample Size

It is estimated that in the SoC arm, we expect 7% of patients to be on combined therapy at 24 weeks. This estimate is based on published data (Koskinas et al³) using the ELIPS study cohort which included exclusively ACS patients. A slightly lower proportion of patients (5%) may be expected to be on combination therapy at 16 weeks.

To detect a meaningful difference in proportions from the SoC group of 0.05 to 0.15 in the DSS with 90% power, we require 744 patients in 24 clusters within each arm.

This calculation assumes a two-sided statistical test at the 5% significance level, ICC of 0.1 and clusters of a similar size (31 for each site).

Justification for ICC of 0.1: Based on the article by Campbell et al.⁴, it would be reasonable for a guideline implementation study within primary care to assume an ICC of the order of 0.1 for process variables and an ICC of less than 0.05 for the outcome variable. This is also in line with empirical estimates obtained from an online database with ICC reported for cluster studies that aimed to change practice.⁵ In the database we examined the hypertension guideline interventions, these varied from 0.048 to 0.064. In addition, we have to consider clustering within country; to be conservative we have assumed an ICC of 0.1.

Based on our experience working in this setting we do not expect any loss of clusters. However, drop out may occur within clusters. As data are extracted from routinely collected electronic healthcare records, we expect missing data to be low as it will only be patients who actively request data collection to stop that will have missing outcome data. Considering a conservative approach⁶ and assuming a loss to follow-up rate of 5%, we need a minimum total sample size of 1568. Considering adjusted numbers per cluster we aim to recruit 792 over 24 clusters per arm (a total sample size of 1584).

Imperial Clinical Trials Unit	ZODIAC STATISTICAL ANALYSIS PLAN – MAIN ANALYSIS	V1 17 th Jan 2024
----------------------------------	--	------------------------------

All calculations were done using PASS 2022 software⁷ and applying a method of “Tests for Two Proportions in a Cluster-Randomised Design”.

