4.8. Follow Up

Follow-up clinic visits will take place as per routine clinical practice. In general these vary but are expected to occur within 3 months for patients accessing cardiac rehabilitation services or at approximately 12 weeks and 16 weeks post index ACS event after discharge in general (1-2 visits). We have not mandated additional visits and the follow up is intended to reflect routine care pathways although the exact timing may vary (maximum 16 weeks). These visits will consist of standard routine care in both randomised groups, with the exception that at DSS sites, staff will be asked to utilise the DSS to assess whether LLT should be further optimised for consented patients.

Routine clinical care includes blood tests for lipids and blood pressure evaluation, evaluation of lifestyle factors such as smoking, exercise, and diet. In the scenario that a cholesterol measurement is unavailable at the time of follow up, patients will be required to have blood tests after the routine follow up. This situation is not specific to this trial and reflects real world clinical practice.

Every effort will be made to ensure follow up data are collected by sites. Where follow up visits have not been attended by Week 16, sites will access the patient's local medical record and/or contact the patient's GP to determine the outcome data status at Week 16. In the event that the local medical record is not available or the GP does not respond, then the patient will be regarded as lost to follow up from the date of the last visit attended or last known prescription from the patient's record for the purposes of censoring.

Note that, for operational reasons, some patients may have data reported at 24 weeks only. These data may be used, where appropriate, to derive or impute the LLT medication status at 16 weeks.

The schedule of events is shown in **Error! Reference source not found..**

Table 1: Schedule of Time and Events

	Baseline	All other visits as per routine care up to 16 weeks
Visit	1	2 onwards
Informed consent	X	
Inclusion & exclusion criteria	X	X
DSS variables	X	X ^a
Demography	X	
CV Medical history	X	
Vital Signs ^b	X	X
Full Lipid Profile	X	X
Medications / LLT	X	X
Lifestyle (smoking, exercise & diet)	X	X
CV events	X	X

^a DSS use optional after Baseline visit

^b Includes height, weight, body mass index, temperature, diastolic and systolic blood pressure, and blood pressure position

5. Variables of Analysis

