We define the primary outcome as missing for anyone who does not have full 16 week follow up, unless they have met the primary outcome prior to the time they are lost to follow up. All patients will be followed up and the primary outcome data will be collected unless the participant requests to withdraw from data collection. Missing data will be examined and quantified; this will include the time of withdrawal and tabulation for reasons for non-completion of study by country, site, and arms. Patterns of missingness and relationship between variables and outcome will be explored. The proportion of clusters (sites) with a missing individual outcome will be calculated and reported as the number of entire clusters with a missing outcome divided by the number of clusters randomised.

As mentioned in Section 4.8, some patients may have data reported at 24 weeks only. These data may be used, where appropriate, to derive or impute the LLT medication status at 16 weeks.

Although mixed models are valid under the missing at random (MAR) assumption, we will use the multilevel multiple imputation (MMI) method to impute values for individuals who have missing outcome data. Missing data can be related to the cluster level or at patient level. We define level 1 variables as those relating to the patient as X and Y and Z, and level 2 variables as those relating to the site as A and B.

Using the *JOMO package* in R with missing outcome data we can use an imputation model which is the same as the analysis model. The JOMO package allows imputation on a mix of multilevel continuous and categorical data.¹⁵ This method uses Markov chain Monte Carlo (MCMC) methods to impute missing values. We will run N imputations and combine the estimates using the mitools package. We will impute N datasets based on the percentage of participants with incomplete outcomes, where N is rounded to the nearest 10. A minimum of 5 imputation datasets will be used. We will include at patient level, intervention, outcome,

Imperial Clinical Trials Unit	ZODIAC STATISTICAL ANALYSIS PLAN – MAIN ANALYSIS	V1 17 th Jan 2024
-------------------------------	--	------------------------------

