8.10. Sensitivity Analysis

Two sensitivity analyses are planned for this study as below:

- A complete case analysis of the primary outcome will be undertaken as a sensitivity analyses. This will include all eligible and randomised patients whose outcomes are

Imperial Clinical Trials Unit	ZODIAC STATISTICAL ANALYSIS PLAN – MAIN ANALYSIS	V1 17 th Jan 2024
----------------------------------	--	------------------------------

available by 16 weeks. Patients in population will be analysed according to the randomised group allocated to the cluster (site) in which they are followed, either SoC or DSS.

- Full ITT analysis including patients who died and incorporating multiple imputation.

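### SAP 4.8 opens a second route to a missing primary outcome that 4.5 and 8.4 leave out, and neither planned sensitivity analysis departs from missing at random

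*SAP*

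**What the plan says.** **Who can be missing.** SAP 4.5 supports its expectation of low missing data by stating that "it will only be patients who actively request data collection to stop that will have missing outcome data". SAP 8.4 repeats the idea: "the primary outcome data will be collected unless the participant requests to withdraw from data collection". SAP 4.8 describes another route. If a patient has attended no visit by Week 16, the site consults the local record or the GP. If the record is unavailable or the GP does not answer, "the patient will be regarded as lost to follow up from the date of the last visit attended", or from the last known prescription, for censoring.

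**What counts as missing.** SAP 8.4 sets the primary outcome to missing for anyone without full 16-week follow-up, unless the outcome was met before loss. SAP 5.2 lets it be met as early as discharge.

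**How missing outcomes are handled.** SAP 8.4 uses multilevel multiple imputation under missing at random. The listed variables are intervention, outcome, age, sex, diabetes, time since first CV diagnosis, site type and country.

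**Sensitivity analyses.** SAP 8.10: "Two sensitivity analyses are planned for this study as below". They are a complete-case analysis and a full ITT analysis that brings back patients who died and again uses multiple imputation. SAP 7.1 and the shells for Tables 45 and 46 show the same two and no others.

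**The concern.** The sections disagree about who will lack an outcome, and the group left out of 4.5 and 8.4 is the one whose missingness is most likely to be related to the outcome. A patient not intensified by discharge who then attends no visit plausibly has less chance of later intensification, although the documents give no rate for such patients.

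The 8.4 rule adds a selection effect of its own. Among patients lost at a given time, the successes so far are kept and the others are set to missing. The imputation then fills those gaps from a pool enriched for success, using variables that do not record where treatment stood at discharge or when contact ended.

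At stake is bias in the primary risk ratio if the effect differs by arm. Because both sensitivity analyses share the assumption, their agreement with the primary result would say nothing about this bias.

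**Working it through.** **1. The plan's own figures.** SAP 4.5 requires, for "0.05 to 0.15 in the DSS with 90% power, we require 744 patients in 24 clusters within each arm", a two-sided 5% test, ICC 0.1 and 31 patients per site.

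- Unpooled n per arm without clustering: (1.960 + 1.282)² × (0.05×0.95 + 0.15×0.85) / 0.10² = 183.9.
- Design effect: 1 + (31 − 1)×0.1 = 4.0, so 183.9 × 4.0 = 735.5. This rounds up to 24 clusters × 31 = 744.
- 5% loss: 744/0.95 = 783.2, rounded up to 784 per arm, or 1568 in total. At 33 per site the target is 792 per arm, 1584 in total.

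All figures reproduce.

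**2. Power is not the issue.** With 33 recruited per site and loss L, m = 33(1 − L), the design effect is 1 + (m − 1)×0.1, and the effective n per arm is 24m divided by it. Unpooled power is 0.904, 0.900, 0.897 and 0.892 at 5, 10, 15 and 20% loss.

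**3. Direction of the selection.** In one arm, let *a* be the proportion intensified by discharge and *b* the proportion intensified later. Let a fraction L be lost at random just after discharge. Then:

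- events seen = a + b(1 − L)
- outcomes seen = 1 − L(1 − a)

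The observed rate is the ratio of the two. It exceeds the true rate a + b whenever a(1 − a − b) > 0, that is, whenever some patients are intensified by discharge and some never are. No link between loss and outcome is needed. If lost patients are also less likely to be intensified later, the excess grows.

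**4. Illustration A: missing patients never intensified (assumed).** Take 5% and 15% as the rates among observed patients, so the planned analysis gives RR 3.00. With missing fractions f, the true RR is 0.15(1 − f_DSS) / [0.05(1 − f_SoC)].

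| f DSS | f SoC | True RR |
|---|---|---|
| 5% | 5% | 3.00 |
| 7.5% | 2.5% | 0.13875/0.04875 = 2.85 |
| 2.5% | 7.5% | 0.14625/0.04625 = 3.16 |

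The unequal rows average the plan's 5%; the split between arms is assumed.

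**5. Illustration B: equal random loss after discharge (assumed).** Split the planned rates into events by discharge and later: DSS 10% + 5%, SoC 2% + 3%. The true RR is 3.00. The split is assumed.

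| Loss | DSS observed rate | SoC observed rate | RR estimated |
|---|---|---|---|
| 10% | 0.145/0.910 = 0.1593 | 0.047/0.902 = 0.0521 | 3.06 |
| 20% | 0.140/0.820 = 0.1707 | 0.044/0.804 = 0.0547 | 3.12 |

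Imputing by arm from the observed rates reproduces these ratios.

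**6. What each analysis would show in illustration B.**

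- Complete case uses the observed rates directly: 3.06 and 3.12 again.
- Full ITT changes only the handling of deaths and imputes the rest as before, so it carries the same error.
- Counting the missing as not intensified gives 0.145/0.047 = 3.09 and 0.140/0.044 = 3.18. It is exact in illustration A but an extreme here, so it should not stand alone.
- Arm-specific shifts recover 3.00. At 10% loss the missing DSS patients have a true rate of 0.05/0.90 = 0.0556 against 0.1593 imputed, a log-odds shift of −1.17. For SoC it is 0.03/0.98 = 0.0306 against 0.0521, a shift of −0.55. At 20% loss the shifts are −1.25 and −0.61.

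**The case against.** The plan handles both routes better than the two sentences suggest. SAP 4.5 budgets 5% for loss to follow-up, the 8.4 rule covers any incomplete follow-up, and Table 21 has separate rows for withdrawn consent and loss. SAP 8.4 also plans reasons for non-completion by country, site and arm, and Table 22 gives timing by arm. All of this stands: the contradiction lies in the stated causes, not in the missingness rule, and no new tabulation is needed.

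Recovery is also planned. Records, GP contact and, where appropriate, 24-week data will supply some outcomes, so the observed patients include recovered non-attenders, and imputation assumes resemblance given covariates rather than outright. That stands too and limits the size.

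A reader might go further in four ways that the documents do not support:

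- *Every non-attender is missing.* Those intensified before loss count as events, including at discharge, and others are recovered.
- *The plan treats missingness as ignorable because only withdrawals cause it.* SAP 4.5 argues only that it will be low; 8.4 mentions missing at random separately.
- *The bias is about 11%.* That needs 15% loss in one arm, 5% in the other and no intensification among the missing, giving 3.35 or 2.68. The average loss is then twice the plan's 5%, and nothing in the documents shows a difference between arms. Staff are unblinded (SAP 4.7), so one is possible, but no more.
- *Significance is at risk.* At the planned effect, counting only missing DSS patients as failures moves z from 3.28 to 3.08 at 5% missing. Losing significance needs a weaker assumed result such as 5% versus 11%, where z falls from 2.16 to 1.99 at 5% and 1.82 at 10%.

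**Conclusion.** The point holds as a minor one. SAP 4.5 and 8.4 state the causes of missing outcomes more narrowly than 4.8. The 8.4 rule makes missingness depend on outcome status at the time of loss, the imputation variables cannot correct for that, and no planned analysis departs from missing at random.

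The size cannot be fixed from the documents. Near 5% loss it is probably modest: from no change to about 5% of the risk ratio in illustration A, and 2% to 4% at 10% to 20% loss in illustration B. Both rest on assumed loss patterns, and B also on an assumed split of events. Both borrow the 5% and 15% planning rates, which SAP 4.5 gives for combination therapy; the primary outcome also counts escalated monotherapy, so actual rates may differ. The direction is not settled either, since illustration A can move the ratio up or down. The documents do not show that the primary result will be biased by a material amount. They show that the plan could not tell if it were.

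**What to change.** - **SAP 4.5 and 8.4:** state both causes of a missing outcome, withdrawal from data collection and loss under 4.8.
- **SAP 8.10:** keep the complete-case analysis and the full ITT analysis. Add (a) an analysis that counts patients lost without prior intensification as not intensified, and (b) a small grid of arm-specific shifts in the log-odds of the imputed outcomes. Illustration B suggests that the grid should reach at least about −1.25 and allow the arms to differ.
- **SAP 7.1 and the shells around Tables 45 and 46:** add matching text and rows.

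The cost is some SAP wording and a little extra analysis on existing data and imputations. Sample size, data collection and the primary analysis do not change. Settling this before unblinding avoids a choice made after the results are known.

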5.1. Baseline Variables

The important demographic variables

1. Age
2. Gender
3. Sex at birth
4. Ethnicity

Lifestyle variables

1. Smoking status (and type of tobacco)
2. Exercise
3. Dietary advice (and if this has been followed)
4. Weight, height and body mass index

Medical/medication history of the patients

Imperial Clinical Trials Unit	ZODIAC STATISTICAL ANALYSIS PLAN – MAIN ANALYSIS	V1 17 th Jan 2024
----------------------------------	--	------------------------------

1. Cardiovascular History
2. Concomitant medication
3. Lipid lowering therapies and their doses

5.2. Primary Efficacy Variable

Proportion of patients with intensification of LLT relative to baseline, regardless of adherence to the DSS, within 16 weeks of index ACS event.

Intensification includes:

- escalation of monotherapy OR
- initiation of combination therapy OR
- escalation of combination therapy

Only commercially available licensed LLT will be considered.

Patients will be considered LLT-naïve on admission if no LLT medications (statins, ezetimibe, bempedoic acid, bile acid sequestrants, evolocumab, alirocumab and inclisiran) are listed on the LLT 'prior to admission' form which captures LLT therapy in the month prior to admission. Patients who are admitted on medicines such as fish oils, nicotinic acid derivatives and fibrates will be considered to be a subgroup of LLT-naïve patients since these agents do not have a clinically significant effect on LDL levels.

Patients who are LLT-naïve on admission will be expected to start on statin monotherapy prior to discharge or an alternative monotherapy prior to discharge, and rarely post-discharge i.e. during follow up. For patients initiated on monotherapy as their first LLT, intensification of therapy in these patients can only occur after starting monotherapy. Therefore, the primary outcome will be met in these patients if they subsequently receive escalation of their monotherapy or start combination therapy during follow up. It is also possible that some LLT-naïve patients may be started on combination therapy at discharge. In this case the primary outcome will be met at discharge.

For patients who are already prescribed LLT prior to admission, they will meet the primary outcome if intensification occurs between admission and discharge or after discharge.

Table 2: Primary outcome definition

Baseline therapy patients recruited with	Meets primary outcome at 16 weeks if the patients is now on
<2 LLT drugs (i.e. 0 to 1)	Combination therapy (2 or more drugs) OR
	Escalated monotherapy (one drug increase in dose, or switch to more potent single drug)

Imperial Clinical Trials Unit	ZODIAC STATISTICAL ANALYSIS PLAN – MAIN ANALYSIS	V1 17 th Jan 2024
-------------------------------	--	------------------------------

>=2 LLT drugs	Escalated combination therapy (e.g. 3 drugs, increase in the potency of one of the drugs if the total number of drugs remains unchanged)
---------------	--

Combination therapy is defined as being on two or more commercially available licensed LLT where treatments overlap by at least one day including:

- Statins (WHO ATC subclass A10AA),
 - Rosuvastatin
 - Atorvastatin
 - Simvastatin
 - Fluvastatin
 - Lovastatin
 - Pravastatin
 - Pitavastatin
- Ezetimibe (Selective cholesterol-absorption inhibitor),
- Bempedoic Acid (Adenosine triphosphate-citrate lyase (ACL) inhibitor),
- Bile acid sequestrant,
- PCSK9 monoclonal inhibitors,
 - Alirocumab
 - Evolocumab
- PCSK9 siRNA therapy (inclisiran)

Escalated therapy includes increase in statin dose or potency (e.g. another statin at a dose which is predicted to have a greater reduction in LDL-C), switching to a more potent combination regimen e.g. statin plus ezetimibe to statin plus PCSK9 Mab, or two drug combination therapy increased to triple therapy.

A bespoke algorithm will be developed to assign primary outcome status by comparing LLT therapy on the 'prior to admission', 'discharge' and 'follow-up' forms. Changes in LLT will be classified as 'escalated monotherapy', 'initiated combination therapy' or 'escalated combination therapy' or 'unchanged/de-intensified' (Appendix A). This classification will be informed by published LDL-lowering potencies of different drugs, different doses and their combinations.⁸⁻¹² The primary outcome is a binary outcome and will be classified as 'Yes' in patients who are classified as receiving 'escalated monotherapy', 'initiated combination therapy' or 'escalated combination therapy' at any time and 'No' if they are classified as 'unchanged/de-intensified' throughout follow up. The algorithm will take into account the most likely foreseen treatment change scenarios. A 10% sample of LLT naïve and non-naïve patients will be checked by blinded clinical review to validate the algorithm. If any unclassified treatment changes are identified that are not captured by the algorithm e.g. due to unforeseen or ambiguous scenarios, these will be reviewed on a case-by-case basis by blinded clinical review to determine whether the change is considered an intensification. Where

Imperial Clinical Trials Unit	ZODIAC STATISTICAL ANALYSIS PLAN – MAIN ANALYSIS	V1 17 th Jan 2024
-------------------------------	--	------------------------------

appropriate, the algorithm will be updated to capture these scenarios. A validation check will be performed on a data extract after 25% of patients are recruited. These checks will be performed separately by country.

5.3. Secondary Efficacy Variables

1. Time to intensification of LLT by week 16
2. LDL-C level closest to 16 weeks
3. Non-HDL-C level closest to 16 weeks
4. HDL-C level closest to 16 weeks
5. TC level closest to 16 weeks
6. Triglycerides level closest to 16 weeks
7. Proportion of patients' reaching target LDL-C levels, <1.4 mmol/L (<55 mg/dL) by week 16
8. Proportion of patients who receive combination therapy by Week 16
9. Proportion of patients who receive escalated monotherapy by Week 16
10. Proportion of patients who receive escalated combination therapy by Week 16

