12.5.3. Binary outcomes

Table 27: Effect of DSS on proportion of patients receiving LLT combination therapy

Patients receiving LLT combination therapy	Trial arm		Adjusted Risk Ratio*	95% confidence interval
	DSS	Control		
N (missing)			x.xx	x.xx to x.xx
n (%)				

*adjusted for country, site type (secondary/ tertiary care/mix of both) and study site

Table 28: Effect of DSS on proportion of patients receiving escalated LLT monotherapy

Patients receiving escalated LLT monotherapy	Trial arm		Adjusted Risk Ratio*	95% confidence interval
	DSS	Control		
N (missing)			x.xx	x.xx to x.xx
n (%)				

*adjusted for country, site type (secondary/ tertiary care/mix of both) and study site

Table 29: Effect of DSS on proportion of patients receiving escalated LLT combination therapy

Patients receiving escalated LLT combination therapy	Trial arm		Adjusted Risk Ratio*	95% confidence interval
	DSS	Control		
N (missing)			x.xx	x.xx to x.xx
n (%)				

*adjusted for country, site type (secondary/ tertiary care/mix of both) and study site

Table 30: Effect of DSS on reaching target LDL-C levels

Patients with target LDL-C levels, <1.4 mmol/L (<55 mg/dL) by week 16	Trial arm		Adjusted Risk Ratio*	95% confidence interval
	DSS	Control		
N (missing)			x.xx	x.xx to x.xx
n (%)				

*adjusted for country, site type (secondary/ tertiary care/mix of both) and study site

12.6.Safety Analysis

Table 31: Adverse Device Effects by trial arm

	DSS arm only	
	No. of patients (%)	No. of events
ADE		
SADE		
USADE		
ASADE		

Table 32: Severity of Adverse Device Effects by trial arm

	DSS arm only	
	No. of patients (%)	No. of events
ADE		
Mild		
Moderate		
Severe		

Table 33: Relatedness of Adverse Device Effects by trial arm

	DSS arm only	
	No. of patients (%)	No. of events
ADE		
Related		
Serious and Related		
Serious, Related and Unanticipated		

Table 34: Type of Adverse Device Effects by trial arm

	DSS arm only	
	No. of patients (%)	No. of events
System Organ Class		
Preferred Term		
.....		

12.7.Subgroup Analysis

Forest plots will be presented for subgroup of interested listed in Section 8.8.

12.8.Exploratory Analysis

Table 35: Exploratory endpoints by Week 16 (all patients)

Endpoint	Trial arm		
	DSS	Control	Overall
Patients achieving target LDL-C level <1.8 mmol/L (<70 mg/dL) by Week 16			
N (missing)			
n (%)			
Patients on combination therapies with three oral LLT or 1 injectable therapy plus one or more oral LLT			
N (missing)			
n (%)			
Mortality before Week 16			

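### The SAP does not fix who can count as escalated combination therapy (secondary item 10), and the all-patient comparison ignores baseline therapy

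*SAP*

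**What the plan says.** Secondary objective 4 (SAP 3.2) compares the arms on the separate types of intensification. The matching variables are items 8 to 10 in SAP 5.3, and item 10 reads "Proportion of patients who receive escalated combination therapy by Week 16". Neither item 9 nor item 10 names a reference form or an eligible group.

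SAP 5.2 describes the category in two places.

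- **Table 2.** Its rows are keyed to "Baseline therapy patients recruited with". The row for two or more drugs reads "Escalated combination therapy (e.g. 3 drugs, increase in the potency of one of the drugs if the total number of drugs remains unchanged". The row for zero or one drug offers "Combination therapy (2 or more drugs) OR" escalated monotherapy, and nothing else.
- **Algorithm text.** It says "A bespoke algorithm will be developed to assign primary outcome status by comparing LLT therapy on the" forms completed for the period before admission, at discharge and at follow-up. Each change is put into one of four classes, and no class is restricted by baseline therapy. The text refers to Appendix A, which is an embedded file whose content is not shown.

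SAP 8.5.3 analyses the binary secondary outcomes in all patients with Week 16 follow-up. The model has arm, country and site type as fixed effects, a random site intercept, and no baseline-therapy term. Table 29, "Effect of DSS on proportion of patients receiving escalated LLT combination therapy", has one N row per arm.

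**The concern.** Take a patient admitted on no lipid-lowering drug, discharged on two, and stepped up at a later visit. Under Table 2 this patient has initiated combination therapy and cannot be an escalated-combination case. If each form is compared with the one before, the same patient also fits the escalated-combination class. The visible text does not choose.

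The choice matters because the DSS is intended to increase initiation. If new starters can score on item 10, the group able to score is partly created by the intervention, and extra initiation alone can raise the item. If they cannot, only the patients already on combination therapy before admission can score. Everyone else is a certain zero, and the ratio moves with any difference between the arms in baseline combination use. In neither case does the planned comparison look at escalation among those who had a combination to escalate.

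Item 9 has a related gap. SAP 5.2 judges treatment-naive patients started on one drug against that first drug, not against their state before admission, so Table 2's baseline key is not the only reference point in use.

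**Working it through.** **1. The plan's own figure.** SAP 4.5 gives 5% versus 15%, two-sided 5% level, 90% power, ICC 0.1 and 31 patients per site.

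- Unpooled two-proportion formula: (1.960 + 1.282)² × (0.05×0.95 + 0.15×0.85) / 0.10² = 183.9 per arm.
- Design effect: 1 + (31 − 1) × 0.1 = 4.0. Then 183.9 × 4 = 735.5, which is 23.7 sites, rounded up to 24 × 31 = 744.
- Loss of 5%: 744 / 0.95 = 784 after rounding up, or 1568 in total. Both stated figures reproduce.

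**2. Inputs for item 10.** Let b be the share on two or more drugs before admission. Let i be initiation of combination among the rest (0.05 control, 0.15 DSS, borrowed from SAP 4.5). Let e be the chance of step-up once on a combination, set equal in both arms so that the DSS has no effect on escalation itself. Let k be the step-up chance of new starters relative to established users. The documents do not give b, e or k; they are assumptions.

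**3. If new starters can score.** P = b·e + (1 − b)·i·e·k. The e cancels in the ratio:

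RR = [b + (1 − b)·0.15·k] / [b + (1 − b)·0.05·k]

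| b | RR, k = 1 | RR, k = 0.5 |
|---|---|---|
| 0% | 3.00 | 3.00 |
| 2% | 2.42 | 2.10 |
| 5% | 1.97 | 1.64 |
| 10% | 1.62 | 1.37 |
| 20% | 1.33 | 1.18 |

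SAP 4.5 phrases the 5% as being on combination therapy: "A slightly lower proportion of patients (5%) may be expected to be on combination therapy at 16 weeks". It can therefore be read as including patients already on a combination at baseline. With b = 5% on that reading, control initiation is 0 and DSS initiation is 10% of all patients. The RR is (0.05 + 0.10k)/0.05, which is 2.0 at k = 0.5 and 1.5 at k = 0.25, inside the same range.

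Events are few. With b = 5%, e = 20%, k = 1:

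- Control: 0.0100 + 0.95×0.05×0.2 = 0.0195, or 14.5 of 744.
- DSS: 0.0100 + 0.95×0.15×0.2 = 0.0385, or 28.6 of 744.
- Power for that difference is about 0.19 at ICC 0.1 and 0.28 at ICC 0.05.

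**4. If only baseline combination users can score.** P = b·e in both arms, so the expected RR is 1.00 for any b above zero. If b is no higher than the 5% to 7% that SAP 4.5 expects later in the control arm, at most 792 × 0.05 = 40 to 792 × 0.07 = 55 patients per arm can score. At least 1 − 55/792 = 93% are then structural zeros.

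A beta-binomial simulation (24 sites of 33 per arm, b = 5%, no stratification or covariates) gives these 95% ranges for the between-arm ratio of patients able to score:

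- ICC 0.02: 0.56 to 1.76
- ICC 0.05: 0.49 to 2.05
- ICC 0.1: 0.39 to 2.50

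With e = 20% in both arms, restricting the comparison to those patients cuts the standard deviation of the log RR from 0.60 to 0.52 at ICC 0.02, and from 0.72 to 0.53 at ICC 0.1. These reductions are 13% (1 − 0.52/0.60) and 26% (1 − 0.53/0.72).

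**The case against.** The strongest reply is that the rule may already exist. The four-way classification is referred to Appendix A, which cannot be read here, and nothing in the visible text says that a new starter who is later stepped up counts as escalated combination. SAP 5.2 defines intensification relative to baseline, 8.3 sets baseline therapy as that before admission, and the phrase about classification at any time belongs to the sentence on the yes/no primary outcome. All of this stands. A reader might infer that the category is open to anyone; the documents leave that possible but do not say it. Table 2, for its part, is formally the definition of the primary outcome and not of item 10. But Appendix A could settle only the classification. The all-patient analysis is set in 8.5.3.

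Secondly, secondary objective 4 asks for the proportions of patients receiving each type of intensification and states no at-risk restriction. An all-patient denominator fits that wording, so it cannot be called a departure from the objective. It remains a weak basis for inference about escalation.

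Thirdly, a ratio of 3.0 is the top of the range and needs almost nobody on combination therapy at baseline. With one or two routine visits expected in 16 weeks, new starters have little time to be stepped up, which favours the lower values. A significant result is unlikely at the power shown.

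Fourthly, the wide ranges in step 4 describe sampling and cluster variation, which the site effect and confidence interval are meant to carry. The simulation ignores stratification and adjustment. That is right: it shows imprecision, some of it avoidable.

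**Conclusion.** The point holds as a gap in definition with a modest analytic consequence. One label has two visible descriptions with different eligible groups, items 9 and 10 do not choose between them, and the planned model takes no account of baseline therapy.

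If new starters can score on item 10, an effect on initiation alone gives an RR of about 1.2 to 3.0. This rests on equal conditional step-up in both arms, k of 0.5 to 1, and baseline combination use from 20% down to 0%. If only baseline combination users can score, there is no bias, but the log RR has a standard deviation of 0.60 to 0.72 where conditioning would give 0.52 to 0.53 (assuming 5% baseline use, 20% step-up and ICC 0.02 to 0.1).

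Two stronger readings are not supported. A reader might infer that item 10 will show a large effect that only reflects initiation; that is one scenario, conditional on an unseen rule and on equal step-up. A reader might also infer that the primary result is compromised; it is not on this point, because a new starter of combination therapy already counts as a yes. Since SAP 9.2 treats secondary results as hypothesis-generating, the severity is minor.

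**What to change.** - In SAP 5.3 and 8.5.3, state that items 9 and 10 follow Table 2's baseline classes. Make Table 2, the algorithm text and Appendix A agree, including on whether items 8 to 10 are mutually exclusive.
- Make the inferential comparison for item 10 among patients on two or more lipid-lowering drugs before admission. Make that for item 9 among those on fewer than two, keeping the post-admission reference that 5.2 already uses for treatment-naive patients.
- In Tables 28 and 29, show those denominators. Keep the all-patient proportions, and later step-up of newly started combinations, as descriptive rows.

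The cost is SAP wording and a baseline filter in two analyses. The class is already tabulated in Table 16, so no new data are needed. The downside is that item 10 would rest on few patients: at the assumed 5%, about 40 per arm over 24 sites, or fewer than two per site. The random-intercept model may not be workable, so the SAP should name a simpler cluster-robust estimate with a confidence interval as the fallback.
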